3.7.2.1 CELL SHIPMENT, PREPARATION FOR ADMINISTRATION – University of Miami

The hCT-MSC cells manufactured at the University of Miami will be shipped prior to initiation of treatment from CRCMPlab at the University of Miami. Upon receiving request for product, a product(s) bag with the appropriate dose is assigned. The preparation of the final product for administration will follow the Standard Operating Procedures maintaining under standardization of procedures. The principal investigator at clinical site will submit a signed request for the final product with date and time of product infusion to processing laboratory prior to the scheduled date. On the day of product infusion, the appropriate number of released frozen bags will be thawed in a 37±1°C water bath. In a biological safety cabinet, the cell suspension is transferred to conical tubes and slowly diluted with buffer containing

Confidential Page **15** of **32**

PlasmaLyte A supplemented with 1% human serum albumin (HSA). The diluted suspension will be centrifuged and the cell pellet will be suspended in the dilution buffer. Viability and cell count will be measure on a cellometer (Nexcellom). The cells will be centrifuged and the cell pellet resuspended in the buffer to a required dose in a total volume of 80mL. Cell dose will be loaded into an infusion bag. The prepared product will undergo a final inspection and release process.

After release, the labeled product will be delivered and issued to the appropriate medical staff in a validated temperature monitored cooler. Clinical coordinator or medical staff maintains custody of the product container to ensure that the product is kept in the proper temperature until it is ready to be removed for infusion.

3.7.2.2 PLACEBO

The placebo for this study will be comprised of 40-80 mL of Plasmalyte-A + 1% Human Serum Albumin (HAS) prepared in an identical container to the one used for cell administration. The placebo product will undergo the same process of sterility testing including release inspection, transport and product custodian.

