sterility (bacT-alert and adventitial virus testing), endotoxin, mycoplasma, P53 mutation, and functional assays (suppression of third party T-cell proliferation and suppression of microglial activation). All assays must pass specifications for release. Stability for the post thaw product is 4 hours at room temperature.

On the day of infusion, the product is thawed, diluted 1:1 with Plasmalyte-A with 5% Human Serum Albumin (HSA), and assessed for total nucleated cell count and viability on a Cellometer. The volume needed for the patient's dose is then calculated, removed and diluted in additional Plasmalyte-A with 5% HSA to 20-40mL and taken to the bedside for infusion. The release specification for viability post thaw is \geq 70%.

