3.7 TREATMENT PROTOCOL PROCEDURES RATIONALE

3.7.1 CLINICAL DOSE SELECTION

The dose for the first 10 patients will be 1 million cells/Kg (with a maximum dose of 100 million cells) with 70% viability post thaw. The dose for the subsequent randomized patients will be 100 million cells (absolute fixed dose) daily x 3 days without adjustment for weight. Analysis of total nucleated cell count and nucleated cell viability is determined in an automated device called a Cellometer (Nexcelom). This dose has been derived from previous clinical studies where hCT-MSCs have been infused at a dose of 2-6 million cells/Kg.

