3.7.2 CELL SHIPMENT, PREPARATION FOR ADMINISTRATION AND INFUSION - Duke

The hCT-MSC cells manufactured at Duke will be shipped prior to initiation of treatment from the Robertson GMP Cell Manufacturing Laboratory at Duke University to the outside treatment site(s) in a dry shipper validated to maintain temperatures <-150 degrees C for 8 days. The cells can be maintained in the dry shipper or transferred to a vapor phase liquid nitrogen freezer which is continuously monitored for temperature. On the day of infusion, the cells will be thawed in a cell therapy laboratory or in a room near the bedside at the infusion site, per standard operating procedure, and aspirated into a sterile syringe containing an equal volume of PlasmaLyte-A with 5% HSA. A TNCC and viability will be performed and cell dose adjusted to 1 million cells/kg with a viability of ≥70% (maximum dose 100 million cells). After this initial dilution, the volume containing the dose for the patient will be further diluted into additional PlasmaLyte-A + 5% HSA to a total volume of 80mL placed into a transfer bag, and transported to the bedside. There they will be administered over approximately 30-60 minutes by gravity. Three daily infusions, 12-36 hours apart will be administered as long as the patient does not have a reaction or other adverse event after the first or second infusion. If an infusion reaction or adverse event related to the hCT-MSC infusion occurs, subsequent infusions will not be administered. For the first 3 consecutive patients on the phase 1 portion of the study there will be a 3 day staggering interval between consecutive patients before the next patient is treated. After the first 3 patients have no detected acute and/or subacute adverse events, the study will continue with open enrollment to complete 10 consecutive patients in phase 1. For phase 2, patients will be randomized 2:1:1 against placebo with patients randomizing to MSCs will be further randomized to receive either Duke of Miami cells.

After release, the labeled product will be delivered and issued to the appropriate medical staff in a validated temperature monitored cooler. Clinical coordinator or medical staff maintains custody of the product container to ensure that the product is kept in the proper temperature until it is ready to be removed for infusion.

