5.2.1 DOSE ADMINISTRATION

- Treatment will start within 72 hours from enrollment or when clinically indicated and the subject meets eligibility
- IV placement
- Premedication with each of the following given approximately 30-60 minutes prior to the hCT- MSC infusion:
 - o 12.5-25 mg diphenhydramine IV;
 - 0.5mg/kg hydrocortisone IV
 - Note: if subjects are currently receiving decadron treatment, hydrocortisone may be omitted at the discretion of the PI.
- hCT-MSC infusion, maximum 100 million cells, infused over approximately 30-60 minutes
- Patient monitoring:
 - Vital signs including BP and respiratory rate will be taken every 15 minutes during the infusion and every 30 minutes for one hour after the infusion
 - Pulse oximetry monitoring during and for 1 hour after the infusion
 - Daily monitoring of pulse oximetry and vital signs in between infusions for a minimum of 4 days following the first infusion.

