9.2 RANDOMIZATION PLAN

In Phase II of this study, a total of 40 participants will be randomized in a ratio of 2:1:1 to placebo, hCT-MSC manufactured at Duke, or hCT-MSC manufactured at Miami. This randomization plan will yield 20 participants on placebo and 10 in each of the hCT-MSC arms. The two hCT-MSC arms will be pooled for analyses comparing treated patients to placebo (see below). The infusion will be blinded so that the medical teams and the patients/LARs will not know which product (placebo, Duke MSC or Miami MSC) the patient receives. There will be unblinded technicians in the laboratories preparing the cells and placebo for infusion, but the final product configuration will be the same for all infusions.

Phase I, Safety 10 patients 1x10^6/kg patient weight (max 100x10^6) Phase II Randomization, Efficacy Placebo hCT-MSCs 10 patients DUKE Fixed dose 100x10^6 10 patients UNIVERSITY OF MIAMI Fixed dose 100x10^6

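### The Phase II blind rests on an identical container and an undefined same configuration; nothing stated hides a cell suspension from a cell-free placebo in the bag or line

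*Combined protocol and SAP*

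**What the plan says.** Section 3.7.2.2 describes the comparator: "The placebo for this study will be comprised of 40-80 mL of Plasmalyte-A + 1% Human Serum Albumin", "prepared in an identical container to the one used for cell administration". It adds that placebo goes through the same sterility testing, release inspection, transport and custody as the cells.

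Section 9.2 sets the blind. Medical teams and patients or their representatives are not to know whether Duke cells, Miami cells or placebo is given. Only the technicians who prepare the products are unblinded, and "the final product configuration will be the same for all infusions". The word configuration is not defined.

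On the active side, section 3.7.1 sets the Phase II dose at "100 million cells (absolute fixed dose) daily x 3 days without adjustment for weight". Section 3.7.2 dilutes the Duke product "to a total volume of 80mL placed into a transfer bag". For the Miami product, section 3.7.2.1 states: "The cells will be centrifuged and the cell pellet resuspended in the buffer to a required dose in a total volume of 80mL". Section 3.4 gives the Duke product a different final volume: "removed and diluted in additional Plasmalyte-A with 5% HSA to 20-40mL and taken to the bedside for infusion".

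**The concern.** An identical container masks the packaging, not the contents. If a bag of cells and a bag of cell-free solution differ in appearance, the plan can be followed exactly and the arm can still be seen.

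The people who would see it are people the plan intends to blind. Sections 3.7.2 and 3.7.2.1 give custody of the released product to the coordinator or medical staff, and section 3.7.2.2 extends this to placebo. Section 3.7.2.3 has the treating physician judge tolerance in real time. Section 5.2.1 adds: "Vital signs including BP and respiratory rate will be taken every 15 minutes during the infusion".

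Two kinds of outcome are at stake.

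- **Safety.** Section 8.2.2 has the treating physician rate causality, and one component of the primary endpoint in section 3.3 is later reactions attributed to the product.
- **Efficacy.** Time to recovery, the main efficacy outcome in section 9.1.2, depends on discharge, need for oxygen and need for other COVID-related care. Each of these leaves room for clinical judgement.

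**Working it through.** The plan gives no figure on this point to reproduce. The check is a comparison of the two bags, a count of the exposure, and a search for any concealment measure.

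**1. Cell concentration (dose / volume)**

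| Product | Source of volume | Calculation | Result |
|---|---|---|---|
| Duke, Miami | 3.7.2, 3.7.2.1 | 100 million / 80 mL | 1.25 million/mL |
| Duke, upper alternative volume | 3.4 | 100 million / 40 mL | 2.5 million/mL |
| Duke, lower alternative volume | 3.4 | 100 million / 20 mL | 5 million/mL |
| Placebo | 3.7.2.2 | 0 / 40-80 mL | 0 |

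Section 3.7.2 writes the 80 mL step next to the weight-based Phase I dose. I take it to carry over to the fixed Phase II dose.

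**2. Volume**

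Against an 80 mL active bag, the placebo may be smaller by up to 80 - 40 = 40 mL, which is half. If the 20-40 mL Duke volume applied, the placebo could be larger by up to 80 - 20 = 60 mL, and the two ranges would meet only at 40 mL. This difference is documented and needs no assumption about turbidity.

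**3. Exposure**

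- Infusions: 40 patients x 3 = 120 at most, fewer if dosing stops early.
- Each infusion runs about 30-60 minutes with vital signs every 15 minutes: 30/15 = 2 to 60/15 = 4 intervals with staff at the bedside.

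**4. Concealment measures stated**

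| Possible measure | In the documents? |
|---|---|
| Identical container | Yes, 3.7.2.2 |
| Same final configuration | Yes, 9.2, undefined |
| Unblinding limited to laboratory technicians | Yes, 9.2 |
| Opaque bag or overwrap | No |
| Sleeved or covered line | No |
| Unblinded person to give the infusion | No |
| Matching, or evidence, of like appearance | No |
| Recording of accidental unmasking | No |

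The containers are called a transfer bag (3.7.2) and an infusion bag (3.7.2.1). Neither is described as clear or opaque.

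**5. Sensitivity of the results**

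With 20 patients per group, one changed judgement moves a proportion by 1/20 = 5 percentage points. Section 9.1.2 expects 30% recovery on placebo, or 0.30 x 20 = 6 patients; one more makes 7/20 = 35%. Section 9.4 also compares each manufacturer's arm of 10 with placebo, where one patient is 1/10 = 10 points. These figures show how little it takes to shift a result. They do not estimate a bias.

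**The case against.** **Appearance is not documented.** A reader might infer that staff can certainly tell the arm by looking. The documents do not support that. They do not say how the suspension or the placebo looks, whether the bag or line is transparent, or at what concentration cells become visible. This stands, and it limits the point to a risk.

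**The container is not the only masking.** A reader might also infer that it is. Section 9.2 adds the common configuration and the limit on who is unblinded, and section 3.7.2.2 adds equal release, transport and custody. This stands as fact. However, none of these steps hides the contents, and an undefined configuration cannot make a cell suspension and a cell-free solution alike.

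**Operating procedures may cover it.** They may, and they are not available here. Where sections 3.7.2 and 3.7.2.1 cite such procedures, they do so for thawing and preparation, not for masking.

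**Little rests on the blind.** Section 9.1.2 makes feasibility the main use of Phase II and calls the analysis descriptive, so no confirmatory claim is at risk. New anti-PRA antibodies, also part of the primary endpoint, are a laboratory result. The documents do not say that the staff at the infusion are those who decide discharge or oxygen need. All of this stands and reduces the consequence. It does not remove it: a descriptive comparison has no protection against biased judgements, and the physician at the infusion does rate causality.

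**Conclusion.** The plan asserts a blind but states no measure that conceals the contents of the bag or line. Followed to the letter, it leaves 1.25 million cells/mL (2.5 to 5 million/mL under the section 3.4 Duke volume) on one side and a cell-free solution on the other, in view of blinded staff for up to 120 infusions. Whether they can see the difference is an assumption. The permitted difference in volume is not.

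The outcomes exposed are the attribution of reactions to the product and the judgement-based parts of time to recovery. The size of any bias cannot be estimated from the documents. The point does not show that the blind fails or that the Phase II results would be invalid. It is a change that should be made, because the remedy is simple and the randomized comparison is of little use for planning a larger trial if its blind is in doubt.

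**What to change.** Add to sections 3.7.2.2 and 9.2:

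- After final inspection and before release, the unblinded technician places every Phase II bag (Duke, Miami and placebo) in an opaque overwrap and sleeves the line as far as flow monitoring allows. The cover stays on until disposal.
- Any accidental unmasking is recorded.
- Placebo is made up to the same final volume as the active product.
- The word configuration is defined so that it covers volume and outward appearance.

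Reconcile the final Duke volumes in sections 3.4 and 3.7.2. If the sponsor prefers not to cover the bags, it should document that the three products look alike in the bag and line.

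**Cost.** Protocol wording, opaque bags and sleeves; dose, sample size and analysis are unchanged. Three practical points need attention.

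- Bedside visual inspection is lost, so inspection must come before covering. Sections 3.7.2.1 and 3.7.2.2 state one for Miami cells and placebo. Section 3.7.2 describes none for Duke cells, so one must be added.
- Section 3.7.2 allows Duke cells to be thawed in a room near the bedside. The covering must then be done there, by an unblinded person and out of sight of the clinical team.
- The infusion runs by gravity under the physician's observation. Any part of the line left uncovered for flow monitoring remains a residual exposure.

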3.7.2.3 INFUSION FLOW RATE

Prior clinical trials have used flow rates up to 30×10^6 hMSC/min where no infusion related toxicity was observed. In the proposed study, the rate of infusion will be conservatively assessed based on patient-specific tolerance of infusion observed by real time assessment by the treating physician. The infusion will be targeted to infuse between 30-60 minutes but definitely before the expiry of the thawed cells (4 hours).

SHOULD THE PATIENT DEVELOP SYMPTOMS SUGGESTIVE OF INTOLERANCE OF THE MAINTENANCE FLOW RATE, THE RATE OF INFUSION MAY BE REDUCED OR THE INFUSION STOPPED AND RESTARTED AT THE DISCRETION OF THE TREATING PHYSICIAN. IF A SERIOUS HYPERSENSITIVITY REACTION OCCURS (HYPOXIA, HYPOTENSION), THE INFUSION MAY BE TERMINATED.

4. ENROLLMENT AND WITHDRAWAL

All patients will receive standard ICU monitoring and all available supportive care for their condition, including oxygen, antibiotics, bronchodilators, mechanical ventilation, antibiotics, etc., and any other FDA approved treatment for COVID-19 infection as per treating physician.

4.1. INCLUSION CRITERIA

- 1. The patient or legally authorized representative (LAR) must have the ability to understand and the willingness to provide a signed and dated informed consent form.
- 2. Age 18 years and over
- 3. The patient agrees to use adequate contraception for the duration of the treatment protocol and for 6 months post treatment.
- 4. Positive RT- PCR testing for COVID-19 nucleic acid using nasopharyngeal swabbing or any other site
- 5. Patient meets ARDS criteria and is on non-invasive or mechanical ventilation or high flow nasal cannula
 - a. bilateral opacities on chest imaging consistent with pulmonary edema

Confidential Page **16** of **32**

- b. A need for positive pressure ventilation or high flow nasal cannula
- c. PaO2/FiO2 ratio ≤ 300 mmHg by arterial blood gas or SpO2/FiO2 imputation.
- d. Infiltrates not fully explained by cardiac failure or fluid overload in the physician's best clinical judgement
- 6. Subjects requiring dialysis as a result of a COVID-19 infection will not be excluded.

4.2. EXCLUSION CRITERIA

- 1. Evidence of multiorgan failure involving one or more organs, excluding the lungs as defined below:
 - a. Presence of shock, defined as MAP < 65 mmHg with signs of peripheral hypoperfusion, or continuous infusion of 2 or more vasopressor or inotrope agents to maintain MAP \geq 65 mmHg.
 - b. Serum bilirubin > 10 mg/dl
 - c. Platelet count < 50,000/ml
 - d. Subjects requiring dialysis as a result of anything other than a COVID-19 infection will be excluded
- 2. Evidence of acquired or congenital immunodeficiency (due to immunosuppressive therapy excluding steroid use for treatment of COVID-19 acute respiratory failure, HIV, previous treatment for cancer, etc.)
- 3. History of metastatic cancer diagnosis or treatment in the past 1 year
- 4. History of previous treatments with MSCs or other cell therapies
- 5. Patient is co-enrolled in any other IND-sponsored clinical trials for COVID-19 or ARDs. Drugs that are administered under emergency use authorizations (EUA) by the FDA are permitted.
- 6. Evidence of pregnancy or lactation
- 7. Moribund patient not expected to survive >24 hours
- 8. Unable/unwilling to deliver lung protective ventilation
- 9. Patient is receiving Extracorporeal Membrane Oxygenation (ECMO)

4.3. PATIENT WITHDRAWAL OR TERMINATION

The patient is free to withdraw from this treatment protocol at any time upon request. The reason(s) for discontinuation of treatment should be recorded.

The treating physician may terminate the treatment protocol if any clinical adverse event (AE) or other medical condition or situation occurs such that continued treatment would not be in the best interest of the patient. The patient will be followed by the treating physician for disease assessments unless the patient withdraws consent for follow up.

5. TREATMENT PLAN

5.1. STUDY SCHEMA

[figure not shown]
This is a 50 patient study in two phases. Phase 1 is an open label safety pilot in 10 patients. Phase 2 is a small exploratory randomized placebo controlled study. The first 10 patients will be consecutively enrolled on an open label phase 1 trial giving 3 doses of hCT-MSCs once a day for 3 days. There will be a hold of 3 days, between each of the first 3 patients on the phase 1 open-labelled portion of the

Confidential Page **17** of **32**

study, to observe for any early toxicity associated with the MSC infusions. If there is not toxicity, the next 7 patients in the phase 1 portion of the study will proceed without any holds between patients.

An interim analysis, for safety will be conducted and reviewed by the Data Safety and Monitoring Board (DSMB) after the first 10 patients have completed treatment and reached the 28 day endpoint. If there are no safety concerns, the trial will proceed with enrollment on the phase 2 portion of the study where the subsequent 40 patients will be randomized in a 1:1 fashion between treatment with MSCs or placebo in a blinded fashion.

Phase 1 / 2a hCT-MSCs for COVID-ARDS

Confidential Page 18 of 32

5.2. DOSE

The hCT-MSC infusion, 1 million cells/kg (maximum 100 million cells) with >70% viability (based on Cellometer), is infused over approximately 30-60 minutes for the first 10 patients. Subsequent patients, randomizing to treatment, will receive 100 million cells/dose per infusion without an adjustment for weight. A second and third infusion of the same number of cells will be given 24 hours (+/- 6 hours) and 48 hours (+/- 6 hours) later, respectively.

5.2.1 DOSE ADMINISTRATION

- Treatment will start within 72 hours from enrollment or when clinically indicated and the subject meets eligibility
- IV placement
- Premedication with each of the following given approximately 30-60 minutes prior to the hCT- MSC infusion:
 - o 12.5-25 mg diphenhydramine IV;
 - 0.5mg/kg hydrocortisone IV
 - Note: if subjects are currently receiving decadron treatment, hydrocortisone may be omitted at the discretion of the PI.
- hCT-MSC infusion, maximum 100 million cells, infused over approximately 30-60 minutes
- Patient monitoring:
 - Vital signs including BP and respiratory rate will be taken every 15 minutes during the infusion and every 30 minutes for one hour after the infusion
 - Pulse oximetry monitoring during and for 1 hour after the infusion
 - Daily monitoring of pulse oximetry and vital signs in between infusions for a minimum of 4 days following the first infusion.

5.3. INTERRUPTION OR DISCONTINUATION OF INFUSION

At the time of the infusion, emergency medications will be located in close proximity to the bedside for use if a hypersensitivity reaction were to occur. The medications will include at a minimum epinephrine, solumedrol and diphenhydramine, albuterol (inhaled), and automated external defibrillator (AED) equipment will also be available. The personnel at the infusion site are trained in resuscitating procedures.

In the event of an infusion-related reaction, e.g. generalized urticaria, cough, dyspnea, wheezing, hypoxia (pulse ox <90), the infusion will be stopped immediately. If medically indicated the patient will be treated with a second dose of diphenhydramine (up to 50mg IV), a second dose of steroids (e.g. solumedrol) (up to 60mg IV). If these signs or symptoms develop, the infusion will not be restarted and the therapy will be aborted. If this occurs after the first or second infusion, the subsequent infusions will not be administered.

If the patient experiences a clinically significant Grade 3 or 4 adverse event (AE) considered by the treating physician to be related to the investigational product or due to the infusion procedure, the infusion will be stopped. Infusion may be restarted at the treating physician's discretion if the AE responds to medical management; otherwise, the infusion should be discontinued permanently.

Confidential Page **19** of **32**

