3.6.1 SAFETY

All patients will be pre-medicated before each dose of hCT-MSCs with a parenteral dose of diphenhydramine (12.5-25mg) and hydrocortisone 0.5 mg/kg IV approximately 30-60 minutes prior to infusion. Using this approach, infusion- associated reactions are uncommon (<1%) and mild. Observed reactions consist of, rash, bronchospasm and rarely, transient hypotension. If an adverse event occurs after the first or second dose, the subsequent doses will not be administered.

The following adverse events, deemed *not related* to the MSC product have been reported in patients receiving BM-MSCs for treatment of graft versus host disease following a blood or marrow transplant where more than 1,000 adults have been treated: increased blood pressure, low blood pressure, difficulty breathing, pain in the abdomen or stomach, abdominal distension, bleeding in the gastrointestinal tract, swelling in legs or arms, nausea, vomiting, diarrhea, dizziness, itching, rash, fever, elevation of blood cells (eosinophils), increase in blood levels of various laboratory values (including alkaline phosphatase, creatinine, lactate dehydrogenase, alanine transaminase and glucose), hypocalcemia, ascites, kidney impairment, hepatomegaly, neutropenia, thrombocytopenia graft versus host disease, chest discomfort, chest pain, oral yeast infection, muscle weakness, joint pain, back pain, cold sweat, headache, and depression.

Other theoretical risks include engraftment and differentiation of transplanted MSCs with ectopic tissue formation. In addition, MSCs in the paracrine and endocrine systems may promote tumor growth and metastasis by diminishing or suppressing the antitumor immunity and inducing neovascularization.

Long term safety information of the use of MSCs is still unknown, but 10 year follow-up in hundreds of treated patients has not revealed any serious problems to date.

Risks associated with the use of diphenhydramine include dizziness, sedation, dry mucous membranes, dryness of the nose and throat, and thick sputum. Allergic reaction can occur, which would, include swelling of the throat and trouble breathing.

Possible side effects of corticosteroids include fluid retention and weight gain, muscle weakness, peptic ulcer; high blood pressure; permanent changes in the bones; increase in infection risk and hyperglycemia.

Confidential Page **14** of **32**

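### Section 5.3 both bars and permits restarting the infusion after a Grade 3 or 4 infusion reaction, and 3.7.2.3 makes termination optional for serious hypersensitivity

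*Combined protocol and SAP*

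**What the plan says.** Section 5.3, second paragraph, deals with infusion-related reactions. After an open list of examples it reads "generalized urticaria, cough, dyspnea, wheezing, hypoxia (pulse ox <90), the infusion will be stopped immediately", and it then says "If these signs or symptoms develop, the infusion will not be restarted and the therapy will be aborted". Remaining doses are also withheld. No severity grade is attached.

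Section 5.3, third paragraph, deals with a clinically significant Grade 3 or 4 adverse event "considered by the treating physician to be related to the investigational product or due to the infusion procedure, the infusion will be stopped". Restarting is then left to the physician's "discretion if the AE responds to medical management; otherwise, the infusion should be discontinued permanently".

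Section 6.1.2 ends treatment after any immediate hypersensitivity reaction.

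Section 3.7.2.3 has two rules. For symptoms of intolerance of the flow rate, "THE RATE OF INFUSION MAY BE REDUCED OR THE INFUSION STOPPED AND RESTARTED AT THE DISCRETION OF THE TREATING PHYSICIAN". For the graver case, "IF A SERIOUS HYPERSENSITIVITY REACTION OCCURS (HYPOXIA, HYPOTENSION), THE INFUSION MAY BE TERMINATED".

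Section 3.6.1 describes past experience: "Observed reactions consist of, rash, bronchospasm and rarely, transient hypotension". On frequency it says that, with premedication, "associated reactions are uncommon (<1%) and mild".

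**The concern.** A severe infusion reaction is an event related to the product or the infusion procedure, so it meets the triggers of both paragraphs of 5.3. One paragraph forbids a restart and the other allows it. Taken literally, mild urticaria ends therapy for good, while a Grade 3 or 4 reaction that settles with treatment may be followed by the rest of the bag.

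What is at stake is the patient at the bedside. A restart would give the remainder of a dose of 100 million cells to someone who has just reacted seriously to it. Infusion reactions are the first component of the primary endpoint (section 3.3), so staff need one rule for handling them.

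**Working it through.** The check is mainly a comparison of texts, event by event, on whether the interrupted infusion may be resumed.

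| Event during infusion | 5.3, second paragraph | 5.3, third paragraph | 3.7.2.3 | 6.1.2 |
|---|---|---|---|---|
| Mild urticaria | Barred (named) | Not triggered | Not named | Treatment ends if it is immediate hypersensitivity |
| Grade 3/4 wheezing, related | Barred (named) | Allowed if it responds | Not named | As above |
| Hypoxia as a serious reaction | Barred (named) | Allowed if Grade 3/4, related and it responds | Termination optional | As above |
| Hypotension as a serious reaction | Not named; the list is open | Allowed if Grade 3/4, related and it responds | Termination optional | As above |

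1. *Overlap within 5.3.* Rows 2 and 3 meet both paragraphs. The third paragraph has no carve-out for infusion reactions, and no sentence ranks the two.
2. *Clash across sections.* Hypoxia is the most direct case: stopping is mandatory in 5.3, while termination is only optional in 3.7.2.3.
3. *Hypotension.* Two of the three reactions named in 3.6.1 have a counterpart in the 5.3 list (rash with urticaria, bronchospasm with wheezing). Hypotension has none.
4. *Is a same-bag restart practicable?* Section 3.7.2.3 targets 30 to 60 minutes and gives thawed cells 4 hours. Then 4 − 1.0 = 3.0 h and 4 − 0.5 = 3.5 h. This is a rough guide only: preparation after thaw shortens it, and an early interruption lengthens it. Section 5.2.1 has blood pressure taken every 15 minutes during the infusion, so a fall can be seen while the bag is running.
5. *How often might it arise?* The documents give no rate for severe reactions. Assume that reactions occur at the stated 1% ceiling and that 1% to 10% of them are severe. Then p = 0.01 × 0.01 = 0.0001 to 0.01 × 0.10 = 0.001. Phase 2 has 20 treated patients and 20 × 3 = 60 cell infusions. The chance of at least one severe reaction is 1 − (1 − p)^n:
   - rate per patient, n = 20: 0.2% to 2.0%;
   - rate per infusion, n = 60: 0.6% to 5.8%.

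   These are chances of a severe reaction, not of a restart or of harm.
6. *Phase 1 experience.* Section 3.6 reports no infusion-related events in 10 patients. The one-sided 95% upper bound is 1 − 0.05^(1/10) = 0.26, so this is reassuring but does not rule such events out.

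**The case against.** The strongest reply is that no one is ordered to do incompatible things. The bar is mandatory, the restart is only permitted, and never restarting complies with every section. A sensible reader would let the second paragraph of 5.3 govern reactions and the third govern other related events. That is probably the intent, but the text does not say so, and the third paragraph's reference to the infusion procedure creates the overlap.

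Three stronger readings are tempting, and the documents do not support them.

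- *A reader might infer that hypotension escapes the no-restart rule.* The list in 5.3 is given as examples only. Section 3.7.2.3 itself classes hypotension as serious hypersensitivity, and 6.1.2 ends treatment after any immediate hypersensitivity reaction. Hypotension is best read as covered.
- *A reader might infer that 3.7.2.3 authorises a restart after hypersensitivity.* Its stop-and-restart wording is tied to flow-rate intolerance. For hypersensitivity it only makes termination optional. It also sits in the background and rationale part, whereas 5.3 is the operative text.
- *A reader might infer that later doses should be withheld after any adverse event until the wording is settled.* Section 3.6.1 and one sentence of 3.7.2 point that way, but the next sentence of 3.7.2 refers to a reaction or a related event. Section 8.1.1 counts adverse events whether or not they are related, apart from unequivocal disease progression. Pressing that rule could cancel doses 2 and 3 for unrelated intensive-care events.

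Existing safeguards also count: an immediate stop for listed reactions, emergency drugs and trained staff at the infusion site, and withheld later doses. The 8.4 trigger of one severe infusion reaction acts after the event and does not govern the restart.

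**Conclusion.** The point holds for the restart rule. For a Grade 3 or 4 infusion-related reaction, 5.3 forbids and permits the same act with no order of precedence, and 3.7.2.3 adds an optional termination where 5.3 and 6.1.2 are mandatory. Hypotension is a matter of clarity, not an open gap.

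The effect is on patient safety only. Sample size, power and endpoint tabulation do not change. Such events should be rare. The 0.2% to 5.8% range rests on an assumed severe share that the documents do not supply, and the conclusion does not depend on it. The point is worth an amendment because the possible harm is serious and the correction is easy.

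**What to change.** - **5.3, second paragraph:** state that it governs all infusion-related and hypersensitivity reactions of any grade. Add hypotension judged to be infusion-related to the examples, because 3.6.1 lists it as an observed reaction. Attribution of a fall in blood pressure stays with the physician.
- **5.3, third paragraph:** limit the restart option to other related Grade 3 or 4 events.
- **3.7.2.3:** make termination mandatory for serious hypersensitivity (*will* in place of *may*). Limit slowing, or stopping and restarting, to rate intolerance without any sign covered by the second paragraph of 5.3.
- **Later doses (optional):** if 3.6.1 and 3.7.2 are harmonised, the sponsor and DSMB should choose the trigger. No interim rule is proposed.

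The cost is one wording amendment, with no new procedures, data fields or patients.
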